**Figure 2. Follow-Up Procedures for Confirmed Orthostatic Hypotension Events**

#### **7.4.4. Evaluation and Follow-Up for Increased, Severe Persistent Joint Pain**

At Screening subjects will provide a daily average pain score (scored with an 11-point NRS via IRT) for the shoulders, hips and knees and any other joint for which a radiograph is obtained (refer to [Section 7.1.1](#)).

In addition, on a weekly basis beginning from Baseline through Week 48, the subject will be asked if he or she experienced new onset or increased pain in a major joint (refer to [Sections 6.2.2.3](#) and [7.1.1.3](#)). If a subject responds that he or she has experienced increased pain in a major joint (Post-Baseline), the subject will be asked to rate his/her pain in that joint on the same 11-point numeric rating scale, using a 24-hour recall (refer to [Section 7.1.1](#)) and will be asked to rate his/her pain in that joint for the remainder of the study.

Joint pain scores recorded electronically will be monitored by site staff to identify subjects who have a pattern of severe pain over several days or a rapid increase in pain. Subjects who record increased pain scores of severe intensity (eg, a score of 7-10 out of 10 on a numerical rating scale) in a knee, hip, shoulder or other major joint which is persistent for at least 2 weeks despite treatment with analgesic medication should be evaluated by the investigator to determine the source of the subject's pain and whether more comprehensive evaluation (eg, radiographic or MRI imaging, orthopedic consultation) of the subject is warranted. An earlier evaluation of the subject can be made at the discretion of the investigator.

At each study visit, systematic site review of the electronically recorded pain scores, and relevant spontaneously reported adverse events will be implemented. In addition, adverse events of joint pain, joint swelling, joint injury/accidents, or fractures will be evaluated by the site personnel.

Subjects meeting the criteria for increased severe or persistent pain or with other clinically significant findings based on the assessment of the investigator are considered to have joint(s) at risk and must have radiographs (x-rays) of the joint(s) obtained and sent to the Central Reader for assessment. MRI scans will not be required but may be obtained if warranted for diagnostic purposes. If warranted, the subject will be referred to an orthopedic surgeon for evaluation.

Radiographic (and any MRI) images collected as part of follow-up procedures for reports of increased severe or persistent pain or clinically significant findings of the investigator will be assessed by the Central Reader for possible or probable events of rapidly progressive osteoarthritis, subchondral insufficiency fractures (spontaneous osteonecrosis of the knee [SPONK]), primary osteonecrosis, or pathological fracture (refer to [Sections 7.4.5](#) and [9.5](#)).

#### **7.4.5. Central Reader and Subject-Level Stopping Criteria for Possible or Probable Joint Safety Events**

Subjects identified through the measures described above (in [Section 7.4.4](#)) who are determined by the Central Reader to have a possible or probable joint safety event (rapidly progressive osteoarthritis (type-1 or type-2), subchondral insufficiency fractures (spontaneous osteonecrosis of the knee [SPONK]), primary osteonecrosis, or pathological fracture), will be withdrawn from treatment and enter the Early Termination Follow-Up

period (refer to Schedule of Activities [Table 2](#) and [Section 6.4](#)). Note: At Screening, vertebral pathologic fracture with less than 50% vertebral body destruction and no spinal canal compromise is allowable. Subjects with radiographic progression of vertebral pathologic fracture to  $\geq 50\%$  of the vertebral body or spinal canal compromise post-Screening will be withdrawn from treatment and enter the Early Termination Follow-Up period (refer to Schedule of Activities [Table 2](#) and [Section 6.4](#)).

The Central Reader will review the radiology images on an ongoing basis and provide assessments to the investigator and Pfizer. For subjects who are identified with a possible or probable event described above and for subjects undergoing total joint replacement for any reason, all images and other source documentation will be provided to the blinded tanezumab Adjudication Committee for review and adjudication of the event. The Adjudication Committee's assessment of the event will represent the final classification of the event (refer to [Appendix 1](#)).

Subjects with adverse event reports of rapidly progressive osteoarthritis (type-1 or type-2), subchondral insufficiency fractures (spontaneous osteonecrosis of the knee [SPONK]), primary osteonecrosis, or pathological fracture, will be withdrawn from treatment and enter the Early Termination Follow-Up period (refer to [Section 6.4](#)).

In addition to Subject-Level Stopping Criteria for Joint Safety Events, this study will also employ Protocol-Level Stopping Criteria. Protocol-Level Stopping Criteria for Joint Safety Events are described in [Section 9.7.1](#).

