**NOTE:**

- Necrosis of the bone secondary to radiotherapy (ie, osteoradionecrosis) and in relation to metastatic disease of the bone (ie, involving the tumor-bone interface) is allowable.
  - Vertebral pathologic fracture with less than 50% vertebral body destruction and no spinal canal compromise is allowable.
  - A treated (eg, fixation) and resolved pathologic fracture of a non-weight bearing bone (eg, humerus) is allowable if not involving a major joint.
13. Signs and symptoms of clinically significant cardiac disease including but not limited to:
- a. Ischemic cardiac disease (eg, unstable angina, myocardial infarction) in the 6 months prior to Screening;
  - b. Surgery or stent placement for coronary artery disease in the 6 months prior to Screening;
  - c. New York Heart Association (NYHA) Class III or IV congestive heart failure or known left ventricular dysfunction with ejection fraction  $\leq 35\%$ , cardiomyopathy, myocarditis in the 6 months prior to Screening;
  - d. Resting tachycardia (heart rate  $\geq 120$ ) or resting bradycardia (heart rate  $\leq 45$ ) on ECG at Screening;
  - e. Any other cardiovascular illness that in the opinion of the investigator would render a subject unsuitable to participate in the study.
14. Subjects who have evidence of orthostatic hypotension based upon replicate orthostatic blood pressure measurements at Screening or at Baseline prior to randomization (refer to [Section 7.3.7](#)). If orthostatic blood pressure change cannot be determined (eg, unable to establish a stable supine systolic and diastolic blood pressure) that subject is not eligible for the study.
15. Diagnosis of a transient ischemic attack in the 6 months prior to Screening or diagnosis of stroke with residual deficits (eg, aphasia, substantial motor or sensory deficits), that would preclude completion of required study activities.
16. History, diagnosis, or signs and symptoms of clinically significant neurological disease including but not limited to:
- a. Alzheimer's disease or other types of dementia;
  - b. Clinically significant head trauma within the past year;
  - c. Peripheral neuropathy or autonomic neuropathy; (Note: Subjects with a stable, chemotherapy-induced peripheral polyneuropathy over the 6 months prior to

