## **8.2. Reporting Period**

For SAEs, the active reporting period to Pfizer or its designated representative begins from the time that the subject provides informed consent, which is obtained prior to the subject's participation in the study, ie, prior to undergoing any study-related procedure and/or receiving investigational product, through the end of the Safety Follow-Up period or through and including 112 calendar days after the subject's last administration of the subcutaneous investigational medication if the subject refuses the protocol defined Follow-Up period.

SAEs occurring to a subject after the active reporting period has ended should be reported to the sponsor if the investigator becomes aware of them; at a minimum, all SAEs that the investigator believes have at least a reasonable possibility of being related to investigational product are to be reported to the sponsor.

AEs (serious and nonserious) should be recorded on the case report form (CRF) from the time the subject has taken at least 1 dose of investigational product through the last subject visit.

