## **8.3. Definition of an Adverse Event**

An AE is any untoward medical occurrence in a clinical investigation subject administered a product or medical device; the event need not necessarily have a causal relationship with the treatment or usage. Examples of AEs include but are not limited to:

- Abnormal test findings;
- Clinically significant symptoms and signs;
- Changes in physical examination findings;
- Hypersensitivity;
- Progression/worsening of underlying disease
- Drug abuse;
- Drug dependency.

Additionally, they may include the signs or symptoms resulting from:

- Drug overdose;
- Drug withdrawal;
- Drug misuse;

- Drug interactions;
- Extravasation;
- Exposure during pregnancy (EDP);
- Exposure via breastfeeding;
- Medication error;
- Occupational exposure.

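### Protocol Section 7.4.5 gives conflicting answers when a vertebral pathologic fracture allowed at Screening worsens but stays below 50%: the Note's withdrawal threshold is not met, yet an adverse event report of pathological fracture withdraws the subject

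*Protocol*

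**What the plan says.** Section 7.4.5 of the protocol contains three statements that bear on a vertebral pathologic fracture.

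1. **Central Reader sentence.** Subjects identified through Section 7.4.4 and "determined by the Central Reader to have a possible or probable joint safety event" are withdrawn. The listed events end with "primary osteonecrosis, or pathological fracture), will be withdrawn from treatment and enter the Early Termination Follow-Up period".
2. **Note.** It follows directly and begins "At Screening, vertebral pathologic fracture with less than 50% vertebral body destruction and no spinal canal compromise is allowable". It continues "Subjects with radiographic progression of vertebral pathologic fracture to" 50% or more "of the vertebral body or spinal canal compromise post-Screening will be withdrawn from treatment".
3. **Adverse event sentence.** After a paragraph on image review and adjudication, the section repeats the list of events and applies the same consequence to any subject with an adverse event report of one of them. Pathological fracture is on that list. The sentence has no exception for vertebral fractures, no percentage and no pointer to the Note.

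The eligibility rules match the first half of the Note. The note to exclusion criterion 12 in Section 4.2 reads "Vertebral pathologic fracture with less than 50% vertebral body destruction and no spinal canal compromise is allowable", so such subjects can be randomized.

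**The concern.** The protocol deliberately admits subjects with a limited vertebral pathologic fracture and sets a threshold for how far it may progress before treatment stops. A threshold of 50% or canal compromise has no purpose unless progression short of it may continue. The adverse event sentence removes that room whenever the progression is reported as an adverse event of pathological fracture. A site that follows the Note and a site that follows the adverse event sentence can both claim compliance while doing opposite things with the same finding.

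At stake are the second and third injections. Section 7.4 states that its subject-level rules operate at those injections, which Section 6.2.2.5 places at Week 8 and Week 16. Drug exposure, and with it the safety data, could differ between sites for a reason unrelated to the subject's condition.

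**Working it through.** The plan gives no figure on this point and no arithmetic applies. The check sets the rules side by side.

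**Can the adverse event route be reached?** Section 8.2 has adverse events recorded "from the time the subject has taken at least 1 dose of investigational product through the last subject visit", so an unchanged fracture known at Screening is not in itself a new event. Section 8.3 lists "Progression/worsening of underlying disease" among its examples of adverse events. Section 8.5 makes an abnormal finding reportable if it has symptoms, needs further diagnostic work or intervention, or is considered an adverse event by the investigator. Growth of an allowed fracture can therefore be reported, and nothing prevents a site from using the term pathological fracture.

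**Case by case:**

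- (a) *Allowed at Screening, unchanged.* The Note does not withdraw. There is no new adverse event. No conflict.
- (b) *Allowed at Screening, worsens, stays below 50% without canal compromise* (for illustration, from 20% to 35%). The Note's threshold is not met, which implies that treatment continues. If the worsening is filed as an adverse event of pathological fracture, statement 3 withdraws. **Conflict.** Statement 1 read alone would also withdraw on a Central Reader finding; the Note beside it looks like a limit on it, but does not say so.
- (c) *Allowed at Screening, reaches 50% or canal compromise.* The Note withdraws, and statement 3 agrees if it is reported. No conflict.
- (d) *New vertebral fracture after Screening, below 50%.* Statement 1 withdraws if the Central Reader finds it, and statement 3 if it is reported. The Note speaks of fractures allowed at Screening and of progression, and does not clearly exempt a new one. Ambiguous, but no clear conflict.
- (e) *Non-vertebral pathological fracture.* Statements 1 and 3 withdraw and the Note does not apply. No conflict.

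The contradiction is firm in one of the five cases, (b), and arguable in one more, (d).

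**Does it reach the primary endpoint?** Section 9.2.1 takes the Week 8 value from the 7 days before the Week 8 visit, so a rule applied at the Week 8 injection acts after those data are collected. For earlier withdrawals, Section 6.4 asks subjects to keep entering cancer pain scores weekly until 16 weeks after the last dose, and Section 9.2.1 imputes only missing data. Imputation around Baseline would need withdrawal before Week 8 for an adverse event together with Week 8 scores that are missing or treated as missing.

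**The case against.** The best reply is that the Note never says that progression below 50% continues on treatment, and never states that its threshold is the sole trigger for vertebral fractures. Read literally, the three statements are cumulative, and meeting any one of them means withdrawal. This stands as a point about wording: continuation is inferred. The inference is nevertheless strong, because under the cumulative reading the threshold would do little work once a smaller progression was reported.

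A second reply is that the case will be uncommon. Section 7.3.9 schedules films of knees, hips, shoulders and other at-risk major joints, and Section 7.1.1.3 defines a major joint as a limb joint, so no spine film is scheduled. Outside Japan the first scheduled post-baseline films come at Week 24, after the last dose. A site might also file the worsening as disease progression, which does not trigger statement 3. Both facts limit how often the case arises. They also show the difficulty: vertebral worsening would tend to surface through symptoms or unscheduled imaging, where adverse event reporting applies, and the outcome then turns on the chosen term.

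Three stronger readings are tempting and are not supported:

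- *That every vertebral fracture below 50% has the conflict.* The Note does not exempt a new fracture.
- *That the primary result is affected.* The timing of the rules, the definition of the Week 8 value and the continued weekly scores all weigh against this.
- *That a count follows from an assumed incidence among the 144 subjects planned for the two arms.* The relevant group is those enrolled with an allowed vertebral fracture that worsens below the threshold and is filed under this term. The protocol gives no rate for any of these steps.

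**Conclusion.** The contradiction is real and narrow. For a vertebral pathologic fracture allowed at Screening that worsens while remaining below 50% and without canal compromise, the Note does not call for withdrawal, whereas the adverse event sentence does once the finding is filed as pathological fracture. Whether doses 2 and 3 are given can then depend on the reporting term.

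The conclusion rests on two things: that the Note's threshold is meant to leave room for lesser progression, and that such progression can be reported as an adverse event, which Sections 8.3 and 8.5 allow. Its size in subjects cannot be derived from the protocol. No effect on the primary endpoint, the sample size or power is shown. It still merits correction, because a mandatory stopping rule should not give two answers for subjects whom the eligibility criteria expressly admit.

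**What to change.** Reconcile the Central Reader sentence, the Note and the adverse event sentence of Section 7.4.5 with the note to exclusion criterion 12. State explicitly whether the Note limits the other two triggers, so that case (b) leads to one instruction whether the worsening is seen on imaging or filed as an adverse event. The same wording can settle whether the Note covers a new vertebral fracture, case (d). Which instruction applies in either case is a clinical decision for the sponsor's clinicians, and none is proposed here.

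The cost is one sentence in an amendment and a memo to sites. No procedure, visit, analysis or sample size changes.

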#### **7.4.6. Procedures for Subjects Undergoing Joint Replacement**

Subjects who have undergone or plan to undergo total joint replacement or other arthroplasty procedure during the study will be discontinued from study treatment.

Subjects who undergo total knee, hip or shoulder joint replacement surgery during the study (Double-blind Treatment Period or Follow-Up Period) will be followed for 24 weeks after the procedure as part of a separate substudy, described in [Appendix 16](#), provided the subject consents.

Transition procedures into the substudy are determined by the timing of total joint replacement surgery:

- Subjects who have undergone or plan an immediate total knee, hip or shoulder joint replacement will be discontinued from the Double-Blind Treatment period and enter into the total joint replacement substudy. At the discontinuation visit, all procedures scheduled for the Week 24 and Week 48 visits should be completed. In addition, if the subject terminates prior to the Week 24 visit, serum and plasma retention samples should be collected, and the **CCI** OR-SDS, **CCI** and PGA instruments should be completed. Female subjects will be advised to continue their contraception regimen during a period of 112 days (16 weeks) after the last dose of SC study medication. Applicable substudy Baseline Visit activities should be completed on the same day as the Study A4091061 End of Treatment Visit.

CCI [REDACTED]

[REDACTED]

[REDACTED]

CCI [REDACTED]

[REDACTED]

[REDACTED]

[REDACTED]

[REDACTED]

CCI [REDACTED]

[REDACTED]

[REDACTED]

[REDACTED]

[REDACTED]

CCI [REDACTED]

CCI [REDACTED]

CCI [REDACTED]

[REDACTED]

CCI [REDACTED]

CCI [REDACTED]

investigator to provide clarity and understanding of the event in the context of the clinical study.

## **8.2. Reporting Period**

For SAEs, the active reporting period to Pfizer or its designated representative begins from the time that the subject provides informed consent, which is obtained prior to the subject's participation in the study, ie, prior to undergoing any study-related procedure and/or receiving investigational product, through the end of the Safety Follow-Up period or through and including 112 calendar days after the subject's last administration of the subcutaneous investigational medication if the subject refuses the protocol defined Follow-Up period.

SAEs occurring to a subject after the active reporting period has ended should be reported to the sponsor if the investigator becomes aware of them; at a minimum, all SAEs that the investigator believes have at least a reasonable possibility of being related to investigational product are to be reported to the sponsor.

AEs (serious and nonserious) should be recorded on the case report form (CRF) from the time the subject has taken at least 1 dose of investigational product through the last subject visit.

## **8.3. Definition of an Adverse Event**

An AE is any untoward medical occurrence in a clinical investigation subject administered a product or medical device; the event need not necessarily have a causal relationship with the treatment or usage. Examples of AEs include but are not limited to:

- Abnormal test findings;
- Clinically significant symptoms and signs;
- Changes in physical examination findings;
- Hypersensitivity;
- Progression/worsening of underlying disease
- Drug abuse;
- Drug dependency.

Additionally, they may include the signs or symptoms resulting from:

- Drug overdose;
- Drug withdrawal;
- Drug misuse;

- Drug interactions;
- Extravasation;
- Exposure during pregnancy (EDP);
- Exposure via breastfeeding;
- Medication error;
- Occupational exposure.

#### **8.4. Medication Errors**

Medication errors may result, in this study, from the administration or consumption of the wrong product, by the wrong subject, at the wrong time, or at the wrong dosage strength. Such medication errors occurring to a study participant are to be captured on the medication error case report form (CRF) which is a specific version of the adverse event (AE) page, and on the SAE form when appropriate. In the event of medication dosing error, the sponsor should be notified immediately.

Medication errors are reportable irrespective of the presence of an associated AE/SAE, including:

- Medication errors involving subject exposure to the investigational product;
- Potential medication errors or uses outside of what is foreseen in the protocol that do or do not involve the participating subject.

Whether or not the medication error is accompanied by an AE, as determined by the investigator, the medication error is captured on the medication error version of the adverse event (AE) page and, if applicable, any associated AE(s) are captured on an AE CRF page.

#### **8.5. Abnormal Test Findings**

The criteria for determining whether an abnormal objective test finding should be reported as an AE are as follows:

- Test result is associated with accompanying symptoms; and/or
- Test result requires additional diagnostic testing or medical/surgical intervention; and/or
- Test result leads to a change in study dosing or discontinuation from the study, significant additional concomitant drug treatment, or other therapy; and/or
- Test result is considered to be an AE by the investigator or sponsor.

Merely repeating an abnormal test, in the absence of any of the above conditions, does not constitute an AE. Any abnormal test result that is determined to be an error does not require reporting as an AE.

### **8.6. Serious Adverse Events**

An SAE is any untoward medical occurrence at any dose that:

- Results in death;
- Is life-threatening (immediate risk of death);
- Requires inpatient hospitalization or prolongation of existing hospitalization;
- Results in persistent or significant disability/incapacity (substantial disruption of the ability to conduct normal life functions);
- Results in congenital anomaly/birth defect.

Medical and scientific judgment is exercised in determining whether an event is an important medical event. An important medical event may not be immediately life-threatening and/or result in death or hospitalization. However, if it is determined that the event may jeopardize the subject or may require intervention to prevent one of the other AE outcomes, the important medical event should be reported as serious.

Examples of such events are intensive treatment in an emergency room or at home for allergic bronchospasm; blood dyscrasias or convulsions that do not result in hospitalization; or development of drug dependency or drug abuse.

Medical device complaints may meet the SAE reporting requirement criteria (see the section on [Medical Device Reporting Requirements](#)). An incident is any malfunction (ie, the failure of a device to meet its performance specifications or to perform as intended; performance specifications include all claims made in the labeling for the device) that, directly or indirectly, might lead to or might have led to the death of a subject, or user, or of other persons, or to a serious deterioration in their state of health.

A serious injury that can cause a serious deterioration in state of health can include:

- a life-threatening illness, even if temporary in nature;
- a permanent impairment of a body function or permanent damage to a body structure;
- a condition necessitating medical or surgical intervention to prevent the above 2 bulleted items;

Examples: clinically relevant increase in the duration of a surgical procedure, a condition that requires hospitalization or significant prolongation of existing hospitalization;

- any indirect harm as a consequence of an incorrect diagnostic or in vitro diagnostic device test results when used within the manufacturer's instructions for use;
- fetal distress, fetal death, or any congenital abnormality or birth defects.

